**Clinical Investigation of the VR-800 Device:
Study Protocol**

NCT Number: NCT04208750

Document Date: 05 AUG 2019

CONFIDENTIAL

TITLE: Clinical Investigation of the Vision-R800 Device. Understanding the Value of High Precision Refractions and Lenses to Optometrists and Patients.

INVESTIGATORS: [name], OD, PhD; [name] OD;
[name], OD, MS

INVESTIGATION SITE: Indiana University

CONFIDENTIAL

RATIONALE AND SIGNIFICANCE:

While all health care may make patients nervous, the optometric examination can be particularly stressful for patients. There is no wonder with the typical exam combining a 'vision test' as well as the general health examination wherein 'bad news' might be expected. Healthcare anxiety has been associated with poor attention (Taylor, 1986) and reduced satisfaction (Court, 2009); the refraction portion of the optometric examination is particularly subject to these problems.

Poor attention to detail during the refraction may contribute to erroneous results. The subsequent glasses are a constant reminder of the quality of the patient's most recent eye examination (indirectly the quality of the optometrist), as patients view their world through the glasses everyday. The stakes are high when the refraction is taking place for the patient to 'answer correctly' and get a good glasses prescription. The presence of healthcare anxiety as related to optometric examination and refraction can result in wasted healthcare resources.

Furthermore, the technology of the phoropter used during the refraction, as well as the precision of glasses made from the prescription, has remained stagnant over the last century while the optics world has improved exponentially. Lenses with precise optics can now be potentially affordably and reliably produced, and technology in the phoropter can be updated to customize refractions to reduce their length and resulting apprehension.

The Vision-R800 phoropter was developed to give the patient a more precise correction of their ametropia during both the refraction and in their resulting glasses prescription. Furthermore, the advanced technology utilized in the Vision-R800 aspires to deliver a more enjoyable patient and doctor experience in determining a glasses prescription.

AIMS:

In an attempt to quantify the value of high precision refractions and lenses to optometrists and patients, as well as understand the technology of the Vision-R800 machine, the specific goals of this study are:

- Quantify the reliability, repeatability, and efficiency of the Vision-R800 phoropter
- Subjectively and objectively compare the refraction experience for the optometrist with the Vision-R800 phoropter as compared to a traditional refraction, from training through prescription writing
- Subjectively and objectively compare the refraction experience for the patient with the Vision-R800 phoropter as compared to a traditional refraction.
- Quantify the value of high precision glasses, in terms of subjective and objective optical performance.

STUDY DESIGN:

This study is a randomized, bilateral, cross-over dispensing study of the full patient experience/process as would occur in the private practice setting, including the refraction and spectacle dispensing. Specifically, “patient” subjects are randomized to experience the traditional refraction and glasses dispensing (0.25D step lenses) or the Vision-R800 refraction and precision glasses (0.01D step lenses). Patient expectation and experience will be gathered prior to, during, and following the experience and lens use. The doctors will be part of the team of investigators. This investigation will run concurrently to phases one and three.

Vision-R800 Machine Details:

The Vision-R800 phoropter systems have been installed in two 4meter exam lanes at the IU School of Optometry.

For all phases of the study, the optometrists will be asked to refract using the “Smart Exam” algorithm with a few minor modifications. First, steps 14 and 15 (binocular vision and stereo) will be removed.

For presbyopes, following testing of distance visual acuity, the algorithm will test JCC and near visual acuity with the add after all of the above distance testing.

Following the refraction, the prescription will be converted from 4 meter testing to infinity using the Vision-R800 conversion equation.

CONFIDENTIAL

Evaluation of Patient Experience (IU experienced doctors refract naive subjects in a crossover dispensing):

Phase two will consist of a new group of naïve patients. A total of 120 patients will be grouped into single vision and progressive addition wearers. Sixty subjects will be included in each of the single vision and presbyopic lens categories, with 30 trying the traditional refraction process and lenses first and 30 trying the new refraction process and lenses first.

1. Young adults: 19-35 years of age
2. Presbyopic adults: 36-80 years of age, progressive addition lens wearers

Following informed consent, the patient will be asked demographic and other subjective/baseline questions about their past experience with refraction and glasses dispensing(s), as well as expectations. These may be video recorded verbal conversations or paper questionnaires. Subjects may be given a wearable heart rate monitor for the remainder of the procedures.

Patients will be randomized to experience either a traditional refraction or a Vision-R800 refraction performed by a study team member (optometrist). The starting point will be the patient's habitual prescription. The refraction will be audio/video-recorded. A final prescription will be generated. Following the refraction, subjective feedback will be obtained.

Patients will be presented with a frame board (of standard, Luxotica frames) and asked to choose a frame. The necessary fitting measurements and adjustments will be made. Spectacle lenses will be manufactured for this frame using prescriptions from either the traditional refraction or the Vision-R800 refraction.

Upon arrival and verification of the edged and assembled glasses, patients will be presented with their spectacles. Spectacles will be dispensed by an experienced optician. At dispensing and at a two-week follow-up visit, subjective and objective vision testing will be completed. Subjects will be asked to wear their glasses at least 6 hours per day.

Subjects will then be randomized to the other type of refraction and all testing procedures will be repeated. All frames and lenses will be provided by the Sponsor. Between the ordering of the second pair of glasses and their dispensing, subjects will be asked to wear their habitual spectacles.

At the final visit, an investigator will show the patient the following prescriptions, in a randomized order, via the Vision-R800 phoropter, and record visual acuity and subjective ratings, while keeping the patient masked. Finally, the patient will be asked their preference for each prescription in paired comparisons, both monocularly and binocularly.

1. Habitual glasses prescription
2. Traditional refraction prescription
3. Vision-R800 refraction prescription

Primary Outcome Measures:

- Test potential claims with patients, as measured by subjective questionnaires
- Assess the benefits of the full Vision-R800 experience from refraction to lenses to the patient, as measured by subjective questionnaires

Other Outcome Measures:

- Vision quality assessments with traditional refraction and Vision-R800 refraction, as measured by visual acuity and subjective vision ratings

Participants:**Enroll up to 128 to finish 120 subjects, equally split into the below groups:**

Young adults: 18+ years of age, single vision glasses wearers

Presbyopic adults: 40-70 years of age, progressive addition lens wearers

*each arm will be targeted to be age, sex and spherical Rx matched, although this is not a requirement

Other subject criteria include:

Not have taken part in other phases of this study

Free of eye disease with an impact on visual acuity or binocular vision abnormalities (by self-report)

The Presbyopic adults must be current adapted progressive addition lens wearers, and the other subject age groups must not be wearing progressive addition lenses.

No formal training in optometry, vision science or in the eyecare field

Must have a wearable pair of glasses from a prescription \leq 2 years old

Must wear glasses at least six hours per day over the last two weeks, and willing to continue wearing glasses at least six hours per day throughout the study

OUTCOME MEASURES:

To achieve the aims outlined above, the outcome measures for this study are broken down into four groups based on where the data is obtained: Patients, Optometrists, Vision-R800 Phoropter and the Glasses.

PATIENTS:**BACKGROUND:**

- Personality Type/attention to detail
- Early adopter to technology (type/age of cell phone?)
 - Would your friends describe you as tech savvy (likert)
- Last eye exam, exam experience
- Age of habitual glasses and where they were purchased
- Current satisfaction with habitual glasses prescription
- Pre-exam expectations
- Habitual prescription including pupillary distance (via lensometry)

DURING REFRACTION:

- Stress/comfort (heart rate, subjective questions, observations from video)
- Casual conversation (observations from the video)
- Step-size of refraction, as calculated by algorithm

AFTER REFRACTION:

- Subjective feedback
 - Overall satisfaction with refraction; likes and dislikes
 - Was there any sort of learning curve with how to respond?
 - Stress level/comfort during refraction
 - How does this compare to what you've had done in the past?
 - Level of confidence with prescription (5-point likert), comments
 - Quality of the refraction (5-point likert), comments
 - Likelihood to purchase glasses from refraction (5-point likert), comments (*following both refractions*)
 - Subjective preference (traditional refraction, Vision-R800 refraction)
 - Overall satisfaction with refraction (5-point likert), comments
 - Stress level/comfort during refraction (5-point likert), comments
 - Level of confidence with prescription (5-point likert), comments
 - Quality of refraction (5-point likert), comments
 - Do you feel the Vision-R800 refraction provides better eyecare? (5-point likert), comments
 - Would you seek out an optometrist with this technology? (5-point likert), comments
 - Do you feel that the lenses manufactured from this technology would be more valuable? (5-point likert), comments

- Did the introduction to this concept live up to your expectations?
- Did you like the technology the doctor had?
- Overall, did you prefer one experience overall?
- Perception of the field of view (no question will be asked about this, and it will not be mentioned; instead it will be noted if this is mentioned in the comments from the participant)
- Monocular and binocular preference between Habitual Rx, traditional refraction endpoint, Vision-R800 refraction endpoint (done by investigator, with subject remaining masked to prescriptions)
- Agreement of quality observed in simulation inside Vision-R800 phoropter versus outside world

VISION-R800 PHOROPTER:

- Final prescription given (traditional refraction vs. Vision-R800 refraction algorithm endpoint and doctor's endpoint)
 - Visual acuity with prescriptions
 - Quality of vision with prescriptions
 - Preference with prescriptions
- Repeatability
 - Within doctor (repeatability of endpoint)
 - Between doctor
 - Improvement with number of refractions completed?
- Path of refraction (what lens choices were given)
- Sensitivity of subject to lens changes (0.25D vs 0.01D)
- Efficiency of algorithm (how many questions were asked)
- Length (time)
- Education level required to do the refraction
- Objective refractions versus subjective refractions

GLASSES:

AT DISPENSING AND FOLLOW UP:

- High Illumination, high contrast logMAR Visual Acuity
- Subjective Questionnaires
 - Quality of vision ratings
 - Glare ratings
 - Halos ratings
 - Ghosting ratings
 - Preference compared to habitual lenses (or control lenses)
- Agreement of quality observed in simulation inside instrument versus outside world

STATISTICAL ANALYSIS:

Repeated measures ANOVA and mixed effects regression models will be used to analyze both the main and interaction effects of outcome measures

PUBLICATION PLAN:

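### The crossover can value the Vision-R800 refraction and 0.01D lenses as a package, but not the part of the fourth aim that is due to lens precision

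*Protocol*

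**What the plan says.** The protocol (AIMS) has four aims. The second and third compare the refraction experience for optometrist and patient. The fourth stands apart and concerns the glasses: "Quantify the value of high precision glasses, in terms of subjective and objective optical performance".

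Under STUDY DESIGN there are two conditions. Participants are "randomized to experience the traditional refraction and glasses dispensing (0.25D step lenses") or to "the Vision-R800 refraction and precision glasses (0.01D step lenses"). In each lens category the sequences are split "with 30 trying the traditional refraction process and lenses first and 30 trying the new refraction process and lenses first". On the lenses themselves: "Spectacle lenses will be manufactured for this frame using prescriptions from either the traditional refraction or the Vision-R800 refraction".

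The final visit adds a comparison inside the instrument: "At the final visit, an investigator will show the patient the following prescriptions, in a randomized order, via the Vision-R800 phoropter". The three prescriptions are habitual, traditional and Vision-R800, and the patient is masked.

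One of the two primary outcomes is worded for the package: "Assess the benefits of the full Vision-R800 experience from refraction to lenses to the patient, as measured by subjective questionnaires".

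The outcome list under VISION-R800 PHOROPTER includes the subject's sensitivity to lens changes of 0.25D against 0.01D. The list under GLASSES has logMAR acuity, ratings of vision quality, glare, halos and ghosting, and preference against habitual or control lenses. The control lenses are not defined.

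In the SAP, the only treatment term in the acuity model is refraction method (LogMAR visual acuity). The symptom analysis compares habitual, Vision-R800 and standard glasses (Subjective preferences and rating-scale data). The sample size is for Vision-R800 against standard refraction (Sample size).

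**The concern.** An aim that asks what high-precision glasses are worth invites a conclusion about lens precision. The two pairs of glasses differ in two ways at once: how the prescription was found, and how finely the lens was made. If patients see better with, or prefer, the Vision-R800 pair, the cause could be the refraction endpoint, the finer step, or both. The worn-glasses data cannot tell these apart.

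The stake is the wording of the results. A primary outcome is to test potential claims with patients, so a claim for precision lenses as such is foreseeable. This trial, as described, would support a claim for the package but not for the lens step alone.

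**Working it through.** **The plan's own figures.** These are not in dispute.
- Paired t-test, standardised effect 0.3, two-sided 5%, 80% power. Normal approximation: ((1.960 + 0.842)/0.3)² = 87.2, so 88. Exact noncentral t: 90, with power 80.4%. The SAP's 90 is reproduced.
- Paired proportions 0.65 and 0.35, taking every pair as discordant: (1.960 + 0.842 × √(1 − 0.09))²/0.09 = 84.8, so 85. The SAP's 85 is reproduced.
- Attrition of 25%: 90/0.75 = 120. Reproduced.

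All of these sizes are for the Vision-R800 versus standard contrast.

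**What the crossover identifies.** Let R = 1 for Vision-R800 refraction and 0 for traditional, and L = 1 for 0.01D lenses and 0 for 0.25D. For a given participant and period,

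outcome = participant + period + a·R + b·L + error.

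| Condition | R | L |
|---|---|---|
| Traditional refraction, 0.25D lenses | 0 | 0 |
| Vision-R800 refraction, 0.01D lenses | 1 | 1 |

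R equals L in every row. The within-participant difference, after allowing for period, estimates a + b and nothing else. A check with four participants over two periods gives 7 columns (4 participant, 1 period, 2 treatment) and rank 6. The missing rank is the separation of a from b. It is a property of the conditions, so a larger sample leaves it unchanged.

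**The final-visit comparison.** Three prescriptions give three pairs: habitual–traditional, habitual–Vision-R800 and traditional–Vision-R800. Each pair sets one refraction against a different one. Masking and random order reduce the influence of expectation and of the exam experience, but no pair holds the endpoint fixed while the step changes.

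**Other places where a lens-step contrast might sit.**
- The phoropter outcome on sensitivity to 0.25D against 0.01D changes names the right contrast. Neither document says how it is measured or analysed.
- The SAP acuity model has no lens-step term, and with these data it could not have one alongside refraction method.
- Phases one and three are mentioned (STUDY DESIGN) but not described.

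**What one extra setting would add.** Take the Vision-R800 endpoint rounded to 0.25D: R = 1, L = 0. The cell matrix (intercept, R, L) goes from rank 2 of 3 to rank 3 of 3. Exact minus rounded is (a + b) − a = b, the step effect at a fixed Vision-R800 endpoint.

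**How precisely.** The documents give no effect size for lens step alone, so these values are assumptions for a continuous rating (paired t-test, two-sided 5%):

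| Assumed effect (SD units) | Completers for 80% power | Power with 90 completers |
|---|---|---|
| 0.3 | 90 | 80.4% |
| 0.2 | 199 | 46.7% |
| 0.15 | 351 | 29.1% |
| 0.1 | 787 | 15.5% |

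Rounding to 0.25D moves a power by at most 0.25/2 = 0.125 D, so an effect below 0.3 is possible.

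**The case against.** The best reply is that the package is what this trial set out to study. The title joins refractions and lenses, the design follows the whole patient process as in private practice, and a primary outcome covers the experience from refraction to lenses. Precision glasses appear only as the product of the Vision-R800 refraction. On that reading, their value against standard glasses is estimable. The SAP's labels are package labels, and it plans no stand-alone claim for lens step.

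Much of this stands. A reader might infer that the fourth aim cannot be answered at all. The documents do not support that: the combined value can be estimated by a randomized within-participant comparison, and this is a legitimate choice. A reader might also infer that step size is measured nowhere. That goes too far as well, given the phoropter outcome on 0.25D against 0.01D changes. A lens-only comparison in phases one or three cannot be excluded either.

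A third tempting step is to say that most of any difference must come from the refraction, because rounding shifts power only slightly. The documents give no spread for the difference between the two refractions, and a share of dioptres is not a share of the effect on acuity, rating or preference. The aliasing needs no such figure.

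What does not stand is the idea that the package reading makes rewording unnecessary. The fourth aim is listed apart from the refraction aims and names the glasses, so a reader will take it as a question about lens precision.

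There is also a fair objection to the added setting: a brief view in the phoropter is not wear, and a null result could be uninformative. That is accepted, and it is why the pair is proposed only as a secondary estimate.

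**Conclusion.** The point holds, for lens precision only. In the described crossover, lens step and refraction method are completely confounded, and the masked final-visit comparison does not separate them. The value of the refraction-plus-lens package is estimable; the part of the fourth aim that is due to lens precision is not, at any sample size. The primary package question is unaffected, and the stated sample sizes are correct for it.

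This rests on two assumptions: that each pair of glasses is made at the step stated for its condition, as STUDY DESIGN implies, and that no lens-only comparison exists in the undescribed phases. It does not rest on any assumed effect size. The correction should be made, because it changes what the trial can be said to have shown about the glasses.

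**What to change.** **Wording, in any case.** Restate the fourth aim as the value of glasses from the combined Vision-R800 refraction and 0.01D lens package against those from the traditional refraction with 0.25D lenses. Attribute every glasses result (acuity, vision quality, glare, halos, ghosting, preference) to that package, not to lens precision. If phase one or three contains a lens-only comparison, point the aim to it. This costs only the edit, and the price is a narrower claim.

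**One masked setting, where the final visit can still be changed.** Add the Vision-R800 endpoint rounded to 0.25D as a coded setting in the existing randomized phoropter comparison, with the single added pair exact versus rounded. Fix the rounding rule in advance. Report the difference with a 95% confidence interval, as a secondary estimate of the optical step effect in the phoropter. This also gives the listed sensitivity outcome a procedure and an analysis.

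The cost is a slightly longer final visit. The pair does not test worn glasses, and its power is limited if the effect is below 0.3.

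The SAP is written in the past tense, gives final groups of 49 and 39, and says the pandemic kept many participants from the final in-office visit. If data collection is closed, only the wording change remains, and it is sufficient to keep the conclusions within the design.

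### Three questionnaire items (better eyecare, would seek out, lenses more valuable) are worded only in the Vision-R800's favour, so agreement with them mixes device effect with wording effect

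*Protocol*

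**What the plan says.** The protocol's Outcome Measures section, under Patients, has three consecutive 5-point items:

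- The first concerns the standard of care: "Do you feel the Vision-R800 refraction provides better eyecare? (5-point likert), comments"
- The second concerns the patient's future choice of practitioner: "Would you seek out an optometrist with this technology? (5-point likert), comments"
- The third concerns the worth of the resulting glasses: "Do you feel that the lenses manufactured from this technology would be more valuable? (5-point likert), comments"

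A further item, "Did you like the technology the doctor had", also runs in one direction but makes no comparison.

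The same list has balanced comparative items. One is the entry beginning "Subjective preference (traditional refraction, Vision-R800 refraction", which offers both methods as answers. Neutrally worded items on satisfaction, stress, confidence and quality follow it. There is also an open question on overall preference and a preference among three prescriptions with the patient masked.

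The protocol's Primary Outcome Measures are questionnaire-based. The first is "Test potential claims with patients, as measured by subjective questionnaires"; the second is to assess the benefits of the whole Vision-R800 experience. No item, hierarchy or success rule is named.

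The SAP (Subjective preferences and rating-scale data) reports response percentages with 95% confidence intervals. It also plans Bayesian estimates of how often patients prefer, have confidence in and see benefit in the Vision-R800, with a Bayes factor. It gives no null value for these items, no Bayes factor threshold and no step for response bias.

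**The concern.** Some respondents agree with whatever proposition they are shown. When every item on a topic states the proposition in the device's favour, that tendency adds to the device's score and nothing in the data removes it. The patient is not masked for these items, because the question itself identifies the technology. The only masking described is for the prescription comparison at the final visit.

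Better eyecare, willingness to seek out a practitioner and greater lens value are the kind of statement that could become a product claim. They also fit the SAP's category of perceived benefits closely. With no primary item designated, nothing stops a high agreement percentage on one of them from being presented as a primary finding. That percentage, and any Bayes factor computed from it, would combine what patients think of the device with how they react to the wording. The planned analysis cannot separate the two.

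**Working it through.** **The plan's own figures.** The SAP (Sample size) gives N=85 for paired proportions of 0.65 and 0.35, N=90 for a paired t-test at effect size 0.3, and N=120 after 25% attrition. All three reproduce, so this point rests on no arithmetic error.

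- N=85, treating every pair as discordant (equivalent to testing 0.65 against 0.50): (1.96 × √1 + 0.8416 × √(1 − 0.09))² / 0.09 = (1.96 + 0.803)² / 0.09 ≈ 84.8, rounded up to 85.
- N=90: paired t-test by the noncentral t distribution, power 0.804 at n=90.
- N=120: 90 / 0.75 = 120.

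**Illustration of the wording effect.** The inputs and their sources are:

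- N = 49 + 39 = 88, the final group sizes in the SAP (Missingness due to COVID-19).
- Two-sided 5% level, borrowed from the SAP's sample size section. The SAP does not set such a test for these items.
- Assumed, not in the documents: the 5-point answers are cut to agree/disagree, the null is 50%, and patients truly have no preference.
- Assumed and varied: a share s of patients agrees with whatever is asked, and the rest split evenly.

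The exact rule at N=88 declares for the device when at least 54 agree (54/88 = 61.4%). With no shift this happens with probability 2.1% in the device's favour. The two-sided rate is 4.2%, but the directional 2.1% is the right comparator for a pro-device result.

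The expected agreement is p = s + (1 − s) × 0.5, and the chance of a significant pro-device result is P(X ≥ 54) for X binomial (88, p):

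| s | p | Chance at N=88 |
|---|---|---|
| 0 | 0.500 | 2.1% |
| 0.05 | 0.525 | 5.9% |
| 0.10 | 0.550 | 13.7% |
| 0.20 | 0.600 | 44.2% |
| 0.30 | 0.650 | 79.7% |

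At the planned N=90 (at least 55 agreeing), the figures for s = 0, 0.10, 0.20 and 0.30 are 2.2%, 14.5%, 46.0% and 81.2%.

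The last row of the table is worth noting. With s = 0.30 the agreement share is 0.65, the larger of the two proportions in the SAP's sample size calculation. On this model, a 15-point wording shift would look like the effect the study was sized to detect.

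**Does balancing remove it?** Suppose half the patients (44 of 88) receive the item worded in favour of the traditional refraction, and answers are scored by the method they favour. The same rule then declares for the device in 2.1%, 1.9% and 1.7% of trials at s = 0.10, 0.20 and 0.30. This models a split ballot. A two-sided scale works on the same principle, because it gives no single proposition to agree with.

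**The case against.** The strongest reply is that these are three items among many, and that the most direct comparisons are sound. The choice between the two refractions, the overall preference and the masked prescription preference are balanced, and yes-saying cannot push a two-option or masked choice towards the device. Confidence, quality and likelihood to purchase are also rated after a refraction in neutral wording, and testing is repeated for the other method. This stands, and it limits the point to the three items. It does not rescue them: the neutral items are neighbours, and none asks about better eyecare, seeking out an optometrist or the value of the lenses.

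A reader might infer that yes-saying alone could hand the trial a positive primary result. The documents do not support that. They do not make these items primary, do not say that five categories are reduced to two, and do not set 50% as the null. The SAP plans Bayesian summaries here and not a 5% test.

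The protocol's list is also an outline without response anchors. A printed scale running from much worse to much better would reduce the bias. None is described, so this remains possible but unshown. Finally, only the first item names the Vision-R800, and the seek-out item asks about intention. Both remarks are fair. Even so, "Would you seek out an optometrist with this technology" has no counterpart for the traditional refraction, and neither does "Do you feel that the lenses manufactured from this technology would be more valuable".

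**Conclusion.** The point holds for three items. They are worded in one direction, no balancing device is described, and the balanced items elsewhere cannot correct them. Because the primary outcomes are left as unspecified questionnaire answers, agreement with these items could be reported as perceived benefit when part of it may be a response to wording.

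The size is illustrative: 13.7%, 44.2% or 79.7% for a significant pro-device result if wording moves an indifferent sample to 55%, 60% or 65%, against 2.1% with no shift. This depends on an assumed shift, an assumed agree/disagree cut, an assumed 50% null and an exact two-sided 5% test at N=88. The documents give no estimate of the shift, so the true bias could be anywhere in this range or outside it.

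It would be wrong to conclude that the comparative questionnaire as a whole is slanted, or that the documents contain a success rule which yes-saying could satisfy.

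**What to change.** For any further use of the questionnaire, put the three items on one balanced 5-point scale, from *traditional much better* through *no difference* to *Vision-R800 much better*, with matching anchors for seeking out and for lens value. Randomise which method is named first and test the answers against the midpoint.

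The SAP describes final group sizes and questionnaire answers already collected, so rewording cannot help those data. Report the three items as descriptive only, print their exact wording and response anchors beside the percentages, and base comparative claims on the balanced and masked preference items. The analysis plan should also name the primary item or items, the null value and the Bayes factor threshold.

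The cost is three reworded items and a short reporting rule. The reworded items will not be comparable with answers already given, and the three items as now worded can no longer support a comparative claim.
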